7.5. Analysis sets

Intent to treat analysis set (ITT)

The ITT analysis set includes all randomized patients.

Modified intend to treat analysis set (mITT)

	QMS document Nerivio TCH-008 Clinical Study Protocol	Doc ID: TEC0250 Revision #: 3.0 Page: 44 of 58
---	--	--

The mITT analysis set includes all ITT participants who had at least 22 days of efficacy assessments in weeks 9-12 of the treatment phase and at least 12 treatments performed in weeks 9-12.

Statistical analysis of the analysis sets

The ITT analysis set will serve as the main set for safety assessments.

The mITT analysis set will serve as the primary set for the efficacy assessment.

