Datasets	
1. Intent to treat analysis set (ITT) The ITT analysis set includes all randomized participants2. Modified intent to treat analysis set (mITT) The mITT analysis set includes all ITT participants who had at least 22 days of efficacy assessments in the last 4 weeks of the treatment phase (weeks 9 through 12) and at least 12 treatments performed throughout weeks 9-12.
Data Analysis	The ITT analysis set will be used for the safety assessments and the mITT analysis set will be used for the efficacy assessments.

	QMS document Nerivio TCH-008 Clinical Study Protocol	Doc ID: TEC0250 Revision #: 3.0 Page: 14 of 58
--	--	--

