6.1.3. Withdrawal / Discontinuation

Participants may withdraw consent at any time and do not have to provide an explanation.

Participant may be withdrawn from the study by the PI or sponsor due to one or more of the following reasons:

- Participant is lost to follow-up
- Refusal of the participant to continue treatment and/or follow-up observations

	QMS document Nerivio TCH-008 Clinical Study Protocol	Doc ID: TEC0250 Revision #: 3.0 Page: 32 of 58
---	--	--

- Serious adverse event
- Participants encountering difficulties with the investigational product (IP) (e.g. cannot tolerate the treatment, unable to operate the application)
- Significant protocol deviation/violation or noncompliance, either by the patient or the investigator
- Decision made by the investigator that termination is in the patient's best medical interest
- Device malfunction
- Other ethical or clinical considerations upon investigator discretion

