6.2. Stimulation program

Nerivio device - The device produces a proprietary electrical signal comprising a modulated symmetrical biphasic square pulse with a modulated frequency of 100-120Hz, pulse width of 400 μ s, and up to 40mA output current (adjusted by the participant). The duration of the treatment is 45 minutes.

Sham device- The device produces electrical pulses of similar width and intensity, but much lower frequency compared to the active device. It produces an electrical signal comprising a modulated symmetrical biphasic and rectangular pulse with a modulated frequency of 0.11-0.2Hz, pulse width of 300-1700 μ s, and up to 34mA output current (adjusted by the participant). The duration of the treatment is 45 minutes. This sham program produces pulses that are perceivable by the user, thus maintaining the blinding, but on the other hand do not intend to activate the CPM as a pain relief mechanism.

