7.2. Endpoints

7.2.1. Primary efficacy endpoint

The primary efficacy endpoint of the study is the difference between the groups in the mean change in the average of migraine headache days per month comparing the 4-week baseline phase (weeks 1 through 4) with the last 28 days (4 weeks) of the treatment phase (weeks 9 through 12). The groups will be compared with the independent t-test.

A migraine headache day is defined as a calendar day with headache that is accompanied by at least one of the following symptoms: aura, photophobia, phonophobia, nausea and/or vomiting; or a calendar day with a headache that is treated with a migraine-specific acute medication.

Subset Analyses

The primary endpoint will also be evaluated stratified by center using a General Linear Model ANOVA test.

A sensitivity analysis of the primary endpoint will be performed to assess the impact of missing data on the study outcome. This will be performed using several possible imputation methods.

Adjustment for other covariates such as demographics or other baseline participant characteristics may be performed by adding these variables into a multivariate linear regression.

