7.6.3. Efficacy analysis

The efficacy endpoints will be assessed on evaluable reports of daily symptoms.

A modified intent to treat analysis set (mITT) will include all ITT participants who had at least 22 days of efficacy assessments in the last 4 weeks of the treatment phase (weeks 9 through 12) and at least 12 treatments performed in the last 4 weeks of the treatment phase (weeks 9 through 12). The efficacy analyses will be conducted on the mITT analysis set. The mITT will be assessed for the mean change in migraine days from the 4-week baseline phase (weeks 1 through 4) to the last 4 weeks of the treatment phase (weeks 9 through 12) and will be compared between treatment groups with a significance level $p<0.05$.

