7.6.7. Interim analysis

One interim analysis is planned after at least 35% of the data is collected (~84 participants in both arms [42 per arm]). The study will continue to the originally planned sample size if the results are favorable (difference between groups in the mean reduction of migraine days of at least 1 migraine day). The interim analysis will be performed on both the mITT and ITT analysis sets, and the enrollment may be stopped due to futility if the interim effects fall below the threshold.

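### The primary efficacy set is a per-protocol set defined by adherence and reporting after randomisation, and no ITT efficacy analysis is stated for the final analysis

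*Combined protocol and SAP*

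**What the plan says.** Section 7.5 defines ITT as all randomised participants and gives it the safety analyses. The set called mITT needs "at least 22 days of efficacy assessments in weeks 9-12 of the treatment phase and at least 12 treatments performed in weeks 9-12". Three places give efficacy to that set:

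- Synopsis, Data Analysis: "the mITT analysis set will be used for the efficacy assessments".
- Section 7.5: "The mITT analysis set will serve as the primary set for the efficacy assessment".
- Section 7.6.3: "The efficacy analyses will be conducted on the mITT analysis set".

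The only efficacy use of ITT is in Section 7.6.7: "The interim analysis will be performed on both the mITT and ITT analysis sets". Section 7.2.1 plans a sensitivity analysis of the primary endpoint for missing data and says of its method only: "This will be performed using several possible imputation methods". Section 7.6.6 scales migraine days up to 28 days for periods in the treatment phase and gives no rule for baseline, although Section 6.3 admits participants with 22 to 27 baseline diary days.

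**The concern.** Both entry conditions are observed only after randomisation, during the weeks in which the primary outcome is measured. The groups compared are therefore no longer the randomised groups. Missing data cannot justify the treatment-count condition, because it removes people whose outcome is fully observed.

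Exclusion could depend on response in one arm and not the other. Section 6.1.3 allows withdrawal when a participant cannot tolerate the device or cannot operate it. Section 6.2 describes the sham pulses as of similar width and intensity, "but much lower frequency compared to the active device" (0.11-0.2 Hz against 100-120 Hz). If exclusion differs in this way, the primary comparison is biased, and the final analysis as written contains nothing that would show it.

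A lesser matter is the missing baseline rule in Section 7.6.6. Read as written, an incomplete baseline diary gives too low a baseline count.

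**Working it through.** **How strict the set is.** Use every other day gives about 14 treatments in 28 days. 12/14 = 85.7%; 11/14 = 78.6%, which is excluded. The diary condition is 22/28 = 78.6%.

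**How many could be excluded.** Section 7.4 needs 234 evaluable participants, expects about 35% discontinuation and enrols up to 375. 234/0.65 = 360; 1 - 234/375 = 37.6%. The plan does not split this loss into before and after randomisation. I therefore assume 15% and 35% exclusion after randomisation, with 35% as the upper case.

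**The plan's own sample size.** For difference 2, SD 3.0, two-sided 0.05 and 80% power, n per arm = 2 × (1.96 + 0.842)² × 3.0² / 2² = 35.3, so 36, not 117. At 117 per arm, power is 99.9%. 117 per arm matches 80% power only at an SD of about 5.4. That discrepancy is a separate matter; it is why two SDs appear in the power figures under the fix.

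**Bias illustration (no true effect, normal outcomes).** Split one arm at its median; the halves have means ±0.798 SD. Exclude a fraction w of the worse half and b of the better half in that arm, and exclude at random in the other.

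Shift in SD = 0.798 × [(1 - b) - (1 - w)] / [(1 - b) + (1 - w)]. With 117 per arm analysed, z shift = shift / √(2/117).

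| Excluded | w / b | Shift (SD) | Days at SD 3.0 | z shift | Type I error |
|---|---|---|---|---|---|
| 35% | 45% / 25% | 0.123 | 0.37 | 0.94 | 15.6% |
| 35% | 40% / 30% | 0.061 | 0.18 | 0.47 | 7.6% |
| 35% | 37.5% / 32.5% | 0.031 | 0.09 | 0.23 | 5.6% |
| 15% | 19.3% / 10.7% | 0.040 | 0.12 | 0.31 | 6.1% |

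With 45%/25% in both arms the mean shift is 0.001 SD and the error 4.6% (20,000 simulated trials, 180 randomised per arm), so there is no bias.

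A second illustration uses unequal retention, 60% against 70%, with excluded participants g days worse than retained ones. The spurious difference is (0.40 - 0.30) × g, or 0.1 to 0.3 day for g = 1 to 3. At SD 3.0 and 117 per arm the error is 5.7% to 11.9%.

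**Baseline prorating.** Assume a true rate of 10 days per 28 and completion spread evenly over 22 to 28 days (mean 25). The raw baseline averages 10 × 25/28 = 8.93, which is 1.07 too low. True reductions of 4.0 and 2.0 would read 2.93 and 0.93; the difference stays 2.0. If the same rule were used for responders, a participant with 25 baseline reports would have to fall to 4.46 days rather than 5 to reach 50%. If completion runs only from 25 to 28 days, the understatement is 0.54.

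**The case against.** Calling mITT the primary efficacy set leaves room for supportive analyses. ITT efficacy is planned at the interim. Imputation would be most useful for people outside mITT, so the sensitivity analysis may have been meant for them. Section 9.1 also lists a separately held statistical analysis plan. All of this is fair, but no final ITT analysis is written down. A missing-data analysis would still not restore a participant with a full diary and 11 treatments. The finding covers the supplied text only.

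On size, no figure in the documents supports the 45%/25% ratio, and milder ratios give much less. In the earlier sham-controlled trial, device-related events were 4.8% against 2.4% (Section 4.2.2) and nobody withdrew for adverse events (Section 4.3.2). Sham pulses are perceivable, and Section 6.6 lists blinding safeguards. This weakens the mechanism, but that trial tested acute use, not eight weeks of scheduled treatment. The 35% case is also an upper bound, because some enrolled participants will fail baseline before randomisation.

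The hypothesis in Section 5.2 concerns treating every other day, so an analysis of adherent use has a rationale. It can be kept as supportive without being the primary comparison.

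The prorating point is a different and smaller defect. Section 7.6.6 speaks of migraine days in the primary analysis, while the responder endpoints count other kinds of headache day, so its effect on responders depends on which rule is used there.

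**Conclusion.** The concern holds. Three sections agree in giving final efficacy to a set selected on adherence and reporting after randomisation, and no final efficacy analysis of all randomised participants is stated. Whether bias occurs, how large it is and in which direction cannot be known from the documents. Under the assumptions shown, one-arm response-related exclusion puts type I error between about 6% and 16%; identical patterns in both arms leave it at 5%. Because this is the primary comparison, it must be fixed before unblinding. The missing baseline rule is minor: it lowers each arm's reported reduction but does not bias the between-arm mean difference in expectation, since baseline gaps arise before randomisation.

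**What to change.** - **Sections 1, 7.5, 7.6.3:** make all randomised participants the primary efficacy set, using all diary days in weeks 5-12 with one pre-specified method. Multiple imputation also covers participants with no diary after baseline; a mixed model for repeated measures would leave them out.
- **Section 7.2.1:** name the set and methods of the sensitivity analysis, and include a missing-not-at-random analysis (delta-adjusted or reference-based imputation).
- **Present mITT set:** keep it as a supportive analysis, labelled per-protocol.
- **Section 7.6.6:** prorate baseline by the same rule, count / reported days × 28.

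The cost is text and analysis work on diary data already planned. Power may fall through dilution. If 35% of 360 randomised have no effect, the difference is 0.65 × 2 = 1.3 days; with 180 per arm, power is about 98% at SD 3.0 and 62% at an assumed SD of 5.4. The 360 leaves room for only 15 baseline failures among 375. If 15% have no effect, the difference is 0.85 × 2 = 1.7 days; with 138 per arm (234/0.85/2), power is about 74% at SD 5.4. At 35%, power equals that of the present plan if excluded participants keep a fraction f of the effect, where 0.65 + 0.35f = √(117/180) = 0.806, so f is about 0.45. These figures treat all outcomes as known; imputation lowers them.

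Participants who stop reporting have no later diary, and Section 13.2 seeks only final-visit observations after consent is withdrawn. The primary method therefore relies on data missing at random, which is why the missing-not-at-random analysis is needed.

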7.6. Statistical analysis

7.6.1. General considerations

Statistical analyses will be performed using a statistical software such as SAS® (SAS Institute, Cary NC, USA), or SPSS statistic program version 27.0 (or higher) software. Baseline demographic and other baseline characteristics, together with safety analyses will be performed on all participants who were randomized. Baseline values are defined as the last valid value prior to treatment.

Where confidence limits are appropriate, a two-sided 95% confidence interval will be constructed.

7.6.2. Demographic and other baseline variables

Demographic and baseline condition related characteristics will be tabulated. Continuous variables will be summarized by a mean, standard deviation, minimum, median and maximum, and categorical variables by a count and percentage.

7.6.3. Efficacy analysis

The efficacy endpoints will be assessed on evaluable reports of daily symptoms.

A modified intent to treat analysis set (mITT) will include all ITT participants who had at least 22 days of efficacy assessments in the last 4 weeks of the treatment phase (weeks 9 through 12) and at least 12 treatments performed in the last 4 weeks of the treatment phase (weeks 9 through 12). The efficacy analyses will be conducted on the mITT analysis set. The mITT will be assessed for the mean change in migraine days from the 4-week baseline phase (weeks 1 through 4) to the last 4 weeks of the treatment phase (weeks 9 through 12) and will be compared between treatment groups with a significance level $p<0.05$.

7.6.4. Safety analysis

Safety and tolerability will be assessed on the ITT analysis set by reviewing of all safety parameters, including adverse events. Serious adverse events, device-related SAEs, adverse events (by type and overall), device-related AE, adverse device reactions and device malfunction rates will be documented. Treatment tolerability, the number and percent of subjects who fail to complete the study and the number and percent of

	QMS document Nerivio TCH-008 Clinical Study Protocol	Doc ID: TEC0250 Revision #: 3.0 Page: 45 of 58
---	--	--

subjects who fail to complete the study because of adverse events will be presented. Time to withdrawal will also be assessed and presented by Kaplan-Meier curves.

7.6.5. Treatment by sites interaction

Poolability across centers may be assessed using logistic regression. Centers with less than 10 subjects will be grouped together by geographical area. If the center term is found significant ($p<0.1$), the reason for this interaction will be further explored. This evaluation may include demographic features, symptoms at presentation, clinical and treatment history, and site comparability in the features found to be associated with the primary endpoint variables. Adjustment for other covariates such as demographics or other baseline subject characteristics may be performed by adding these variables into a logistic regression model. The analysis may be repeated for US sites vs. out of US (OUS) sites, if applicable.

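### Section 7.6.5 is headed as a treatment-by-site interaction check but applies its p<0.1 trigger to the centre term; no treatment-by-centre term is named anywhere

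*Combined protocol and SAP*

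**What the plan says.** The section title is "7.6.5. Treatment by sites interaction". Its first sentence makes the check optional and names the model: "Poolability across centers may be assessed using logistic regression". Small centres are pooled first: "Centers with less than 10 subjects will be grouped together by geographical area". The trigger is "If the center term is found significant", at p<0.1, after which "the reason for this interaction will be further explored". The section allows the analysis to be repeated for US against OUS sites.

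The only other centre analysis of the primary endpoint is in section 7.2.1: "The primary endpoint will also be evaluated stratified by center using a General Linear Model ANOVA test". It does not list its model terms. The primary comparison in that section is separate: "The groups will be compared with the independent t-test". Section 7.7 randomises 1:1 in blocks stratified by centre.

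**The concern.** The title and the consequence speak of an interaction, but the term tested is the centre term. These answer different questions. A centre term asks whether the change in migraine headache days, averaged over both arms, differs between centres. A treatment-by-centre term asks whether the active-minus-sham difference does. Only the second bears on whether the treatment effect can be pooled. With 1:1 allocation blocked by centre, a difference that both arms share does not by itself bias the treatment comparison.

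A programmer who follows the text would fit and test the centre coefficient. Two errors are then possible: a shared centre difference is reported and explored as an interaction, or a treatment effect that varies between centres goes unflagged. The same holds for US versus OUS. The term would show whether the regions report different changes, not whether the device works differently there.

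**Working it through.** Section 7.6.5 gives no operating figure to reproduce, so the check is to compare the two terms under stated conditions.

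**Inputs from the plan.** Threshold p<0.1 (7.6.5); 1:1 allocation within centre (7.7); 234 evaluable participants and SD 3.0 (7.4).

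**Assumptions.** The number of centres and the spread between them are not given. I take K = 12 centres, as in the earlier pivotal study TCH-003 (7 + 5 sites, section 4.2.2), with m = 10 per arm per centre, so n = 240. The residual SD σ is 3.0, or 5.4 as a second value. The second is used because a difference of 2 with SD 3.0 needs 2 × (1.960 + 0.842)² × 9/4 = 35.3, so 36 per arm, while 117 per arm fits an SD of about 2 × √(117/2)/2.802 = 5.46. That mismatch is a separate matter; here it only sets a range.

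**The two tests.** SS_C, SS_I and SS_E are the sums of squares for centre, interaction and error.
- Centre term, additive model: F_C = [SS_C/(K−1)] / [(SS_E + SS_I)/(n−K−1)], with 11 and 227 df.
- Treatment-by-centre term: F_I = [SS_I/(K−1)] / [SS_E/(n−2K)], with 11 and 216 df.
- The 10% critical value is 1.60 for both.

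Let τ be the SD between centres of the centre mean (averaged over arms), and δ the SD between centres of the treatment effect. The numerator mean squares have expectation
- centre: σ² + 2mτ² = σ² + 20τ²
- interaction: σ² + (m/2)δ² = σ² + 5δ²

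The centre numerator does not contain δ, and the interaction numerator does not contain τ.

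**(a) One common effect (δ = 0), centre means differ.** The centre term fires with probability P(F > 1.60/R), where R = 1 + 20τ²/σ².

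| τ (days) | σ | R | 1.60/R | Centre term fires | Interaction term fires |
|---|---|---|---|---|---|
| 0.5 | 3.0 | 1 + 5/9 = 1.56 | 1.03 | 42% | 10% |
| 0.5 | 5.4 | 1 + 5/29.16 = 1.17 | 1.37 | 19% | 10% |
| 1 | 3.0 | 1 + 20/9 = 3.22 | 0.50 | 90% | 10% |
| 1 | 5.4 | 1 + 20/29.16 = 1.69 | 0.95 | 49% | 10% |

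Simulation of the same layout agrees to within about two points (41–42%, 18–19%, 90–91% and 49–51%).

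**(b) Effect differs with δ = 2 days, centre means identical (τ = 0).** This needs the two arms to move in opposite directions by equal amounts at each centre. For the interaction term, R = 1 + 5 × 4/σ² = 3.22 or 1.69, so it fires in 90% or 49%. For the centre term, the heterogeneity only enlarges the residual. At σ = 3.0 the residual mean square becomes about (216 × 9 + 11 × 29)/227 = 9.97 instead of 9, and the rate drops below nominal to 6%. At σ = 5.4 it is 9%.

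**(c) Effect differs with δ = 2 days in more ordinary patterns.** If only the active arm varies, the centre mean moves by half the effect, so τ = 2/2 = 1. If the arms vary independently, each with variance 2, then δ² = 4 and τ² = (2 + 2)/4 = 1. Either way both numerators have expectation σ² + 20. Simulated rates, centre against interaction, are 86–88% against 90–91% (σ = 3.0) and 46–48% against 48–50% (σ = 5.4).

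**(d) Other layouts and the logistic model.** With 6 to 12 equal centres, about 234 participants and σ = 3.0:
- centre levels of ±1 day with a common effect: 97–99% against about 10%
- effects of 0 and 4 days in alternate centres with equal centre means: 6–7% against 96–99%
- the same effects with equal sham means: 93–99% against 96–99%

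In a logistic version for an assumed responder outcome with 6 or 8 centres, a common odds ratio with shifted centre levels gives 95–97% against about 13%. Responder rates of 15% versus 55% in half the centres and 35% versus 35% in the rest give 9–10% against 80–83%. The fault is the term tested, whichever model is used.

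**The case against.** The fair defence is that the centre term is shorthand. The title, the subject of poolability and the reference to an interaction all point to the treatment-by-centre term, and section 9.1 lists a statistical analysis plan kept apart from the protocol that may spell it out. This stands as a statement of likely intent. It does not remove the problem: the text names one term, that term is not the interaction, and the documents available name no other.

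The size is also open to challenge, and much of that stands. The 6% to 9% miss rate belongs to one extreme pattern that nothing in the plan suggests. The false-alarm rate depends on how far centre means differ, and a constant reporting habit at a centre largely cancels in a change from baseline. A between-centre effect SD of 2 days is as large as the planned mean effect. At 1 day the interaction test itself would fire in only about 42% (R = 1 + 5/9) or 19% (R = 1 + 5/29.16) of trials.

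A reader might go further and infer that the plan would generally overlook differing effects, or that the primary result rests on a faulty poolability decision. The documents support neither. Case (c) shows detection close to that of the interaction test. Section 7.6.5 says only that the check may be done and that a finding will be explored; it neither bars pooling nor alters the t-test.

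**Conclusion.** The point holds as a fault in what 7.6.5 specifies, of moderate weight. Followed literally, the rule treats shared centre differences as an interaction more often than its nominal 10%: about 19% to 42% of trials with a centre SD of 0.5 day and 49% to 90% with 1 day. It can miss an effect that varies between centres when centre means stay similar, but does about as well as the interaction test when only one arm varies or the arms vary independently. The percentages rest on an assumed layout of 12 centres of 20, assumed spreads and a linear model. That the two terms respond to different quantities does not depend on those assumptions.

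The primary t-test is untouched. What is at risk is any statement on poolability, or on US versus OUS sites, drawn from this check. Choosing the relevant term after unblinding would be post hoc.

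**What to change.** In section 7.6.5:
- Replace logistic regression with a linear model of change in monthly migraine headache days on treatment, centre and treatment × centre, keeping the planned grouping of centres with fewer than 10 subjects. Changing only the name of the term would leave a logistic model attached to a continuous outcome.
- Apply the p<0.10 rule to the treatment-by-centre term only, and state that a significant centre term alone does not count against pooling.
- Show the active-minus-sham difference for each centre or centre group.
- For US versus OUS, use the treatment-by-region term.

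The cost is a few sentences and one extra model term, with no new data, no extra participants and no change to the primary analysis. The drawback is that an interaction test has limited power, so a non-significant result should be read alongside the centre-specific estimates and not as proof of a uniform effect.
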